- In case of consecutive 2 skipped doses, the treatment discontinuation should be considered (general rule). In some exceptional circumstances (e.g. COVID-19 like pandemic situation), sponsor must be contacted for alternative option. If 2 consecutive doses of study medication are missed, the patient may recommence the study treatment if considered safe as per the investigator's discretion and the patient does not meet any of the discontinuation criteria".

During the COVID-19 pandemic, physical visits to the sites may need to be restricted to ensure patient safety. Based on a thorough assessment of the benefits and risks, the investigator may still decide to continue the trial treatment and trial medication may be shipped to the patient's home if acceptable according to local law and regulations, for more details see [section 6.2.2](#)

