PoCC will be established if at least one model is statistically significant, rejecting the null hypothesis of a flat dose response relationship for percentage change in body weight jointly over the candidate dose response models, with a contrast test controlled for the family-wise type I error rate at one sided $\alpha = 2.5\%$.

If PoCC is established, the statistically significant (best fitting) model(s) from the above candidate set will be refitted to the data to generate new estimates for all model parameters from the data. The target dose(s) will be estimated from the best fitting model(s) by incorporating information on the minimum clinically relevant effect and accounting for safety.

The primary analysis of percentage change from baseline in body weight at Week 46 will be performed using the FAS and will assign patients to the randomised maintenance dose. It will include all available data without regard to whether patients started the maintenance period

with a lower dose than the one randomised to. For patients who discontinued treatment early, a distinction will be made according to whether this is due to a COVID-19 pandemic-related reason or not. Patients who discontinued treatment early due to a pandemic-related reason (e.g. direct COVID-19 infection, drug supply issue, site closure, quarantine preventing site access) will have data handled after discontinuation as if they were missing. Patients who discontinued treatment early for any other reason will have all available data included after discontinuation, irrespective of whether such patients subsequently received any permitted anti-obesity treatments.

The above approach to the primary analysis specifies a hypothetical strategy for the intercurrent event of pandemic-related early treatment discontinuation, and a treatment policy strategy for the intercurrent event of non-pandemic-related early treatment discontinuation.

The primary endpoint will be summarised descriptively overall, and by pre-specified subgroups (to be specified in the TSAP, but which may include e.g. subgroups based on gender, baseline BMI and age at screening).

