7.4 PRIMARY ENDPOINT(S)

Descriptive summaries of body weight and percentage change from baseline will be presented over time. These summaries will be produced in each of the following different ways:

- FAS, planned maintenance treatment, all data (i.e. both on-treatment and off-treatment as defined in [Section 6.1.6](#), and irrespective of any anti-obesity medications subsequently introduced for patients who discontinued treatment early)
- FAS, planned maintenance treatment, all data (as above) but censored for any early treatment discontinuation related to the COVID-19 pandemic (either direct COVID-19 infection or other indirect pandemic-related reason)
- FAS, planned maintenance treatment, on-treatment data only
- FAS, actual maintenance treatment, all data censored for COVID-19 related treatment discontinuation
- FAS, actual maintenance treatment, on-treatment data only.

The first descriptive summary above, which uses all available body weight data, will be repeated split at each time point according to whether the contributing data are on- or off-treatment.

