7.4.1 Primary analysis of the primary endpoint(s)

The primary analysis of the primary endpoint will be performed on the FAS, using planned maintenance treatment, and including all data censored for COVID-19 related early treatment discontinuation. This specifies a hypothetical estimand strategy for the intercurrent event of pandemic-related early treatment discontinuation, and a treatment policy strategy for the intercurrent event of non-pandemic-related early treatment discontinuation.

A COVID-19 related early treatment discontinuation is defined as either of the following situations):

- Direct patient COVID-19 infection: Reason for early treatment discontinuation is given on the End of Treatment eCRF page as “Adverse Event” and a treatment-emergent AE of “COVID-19” is recorded.
- Other COVID-19 restriction (site access, drug supply, quarantine, etc) which meant that study treatment could not be continued: Reason for early treatment discontinuation is given on the End of Treatment eCRF page as “Other” and the supporting comments indicate clearly “COVID-19”.

Further, “censored for” COVID-19 related treatment discontinuation is clarified to mean in practice that for patients who had a COVID-19 related treatment discontinuation (and only for these patients), only the on-treatment data will be used, as defined in [Section 6.1.6](#).

Missing data will be modelled based on what was observed up to the occurrence of these intercurrent events using direct likelihood approaches, which is a valid approach under the assumption that data are MAR.

An MMRM will be fitted to the percentage change in body weight values at each scheduled week (calculated as per [Section 6.7](#)) for this purpose. The MMRM will include fixed effects for baseline body weight as a continuous linear covariate, and treatment, gender, visit, treatment by visit interaction and baseline by visit interaction as factors. The Kenward-Roger approximation will be used to estimate the denominator degrees of freedom.

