7.9 ANALYSIS OF COVID-19 IMPACT

There is currently an outbreak of respiratory disease, COVID-19 worldwide which has impacted the conduct of this trial. This public health emergency has raised more difficulties for patients to meet protocol-specified procedures, including administering or using the investigational product or adhering to protocol-mandated visits and laboratory/diagnostic testing. Site personnel or trial patients are also under the risk to get infection with COVID-19.

Consequently, there are unavoidable protocol deviations due to COVID-19 illness and/or COVID-19 public and individual health control measures. To assess the impact on patients' safety and drug efficacy in this trial, the following analyses are planned:

[REDACTED]

Summary tables and listings of AEs of SARS-CoV-2 infection will be produced. The tables will include an overall summary, a summary by primary SOC and PT, a summary of relevant AEs which led to early treatment discontinuation, and a summary of relevant serious AEs. For

this purpose, “SARS-CoV-2 infection” is defined by the broad BICMQ of SARS-CoV-2 infections with search ID 32010051. The broad BICMQ differs from the narrow BICMQ only by the inclusion of the PT for “Suspected COVID-19”.

AEs related to SARS-CoV-2 infection will also be summarised and listed. For this purpose, “related to SARS-CoV-2 infection” is defined by the MedDRA broad SMQ for COVID-19.

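### SAP 7.4.1 identifies COVID-19 treatment stops by eCRF label rather than by cause, so a stop can fall under the wrong estimand strategy, in either direction

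*SAP*

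**What the plan says.** Protocol 7.2.2 applies the hypothetical strategy to stops "due to a pandemic-related reason (e.g. direct COVID-19 infection, drug supply issue, site closure, quarantine preventing site access") and the treatment policy strategy to all others. The list of examples is open and is not tied to any eCRF field. SAP 7.4, on the descriptive summaries, is similarly wide: "either direct COVID-19 infection or other indirect pandemic-related reason".

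SAP 7.4.1 keeps both strategies but identifies the event by two limbs:

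- **Direct:** the End of Treatment reason is given "as “Adverse Event” and a treatment-emergent AE of “COVID-19” is recorded".
- **Indirect:** the reason is given "as “Other” and the supporting comments indicate clearly “COVID-19". Site access, drug supply and quarantine are named as examples.

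A patient who meets either limb contributes only on-treatment data, which run to 28 days after the last dose (SAP 6.1.6). Every other patient contributes all data. SAP 7.5.2 uses the same censoring for the responder endpoints.

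For its COVID-19 safety tables, SAP 7.9 says that SARS-CoV-2 infection "is defined by the broad BICMQ of SARS-CoV-2 infections with search ID 32010051". It adds: "The broad BICMQ differs from the narrow BICMQ only by the inclusion of the PT for “Suspected COVID-19". One planned table shows these AEs where they led to early treatment discontinuation. SAP section 4, on changes to the planned analysis, does not mention the rule in 7.4.1.

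**The concern.** The protocol defines the intercurrent event by its cause. The SAP recognises it by how the form was filled in. The two can part in three ways:

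1. A pandemic cause may sit under an End of Treatment reason other than 'Other', and the indirect limb then fails whatever the comment says.
2. An infection may be recorded under a term that the 7.9 query covers but 7.4.1 does not name.
3. The direct limb asks only that a COVID-19 AE exists. It does not ask that this AE caused the stop, or was near it in time.

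The first two leave off-drug weights in the primary analysis that the estimand says to set aside. The third discards off-drug weights that the estimand says to keep. The affected values feed the primary MMRM, then MCPMod, and also the responder analyses. Off-drug weights should often exist, because protocol 6.2.3 asks patients who stopped early to return every 4 weeks for weighing until Week 46. The 7.9 table could also show a SARS-CoV-2 discontinuation that the primary analysis handled as non-pandemic.

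**Working it through.** **Step 1. Set the definitions side by side.**

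| Stop | Protocol 7.2.2 | SAP 7.4.1, read literally | Agree? |
|---|---|---|---|
| Quarantine or supply problem, filed as 'Other' with a clear comment | Hypothetical | Censored | Yes |
| Pandemic-caused missed doses, more than 4, filed under a reason other than 'Other' | Hypothetical | Not censored | No |
| Infection stop, AE recorded as 'Suspected COVID-19' | Hypothetical, if a suspected case counts | Not censored | No, or undefined |
| Stop for an unrelated AE, with a COVID-19 AE at another time on treatment | Treatment policy | Censored | No, opposite direction |
| Any of these with no weight later than 28 days after last dose | – | Same data either way | No effect |

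The second row has a basis in the protocol. Section 4.1.4 classes more than 4 skipped doses as non-compliance that ends treatment, and section 3.3.4.1 lists missed doses among the reasons to stop.

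**Step 2. Reproduce the plan's own figure, to anchor the size.** Protocol 7.5 gives n = 70 per arm, SD = 7.0, a top-dose effect of -10.0, a target difference beyond -9.0, and 82.8% probability of success for the linear shape.

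- Doses are 0, 0.6, 2.4, 3.6 and 4.8 mg, with mean 2.28 and sum of squared deviations 16.128.
- SE of the fitted difference at 4.8 mg = 4.8 × 7 / √(70 × 16.128) = 33.6 / 33.6 = 1.00.
- P(fitted difference < -9) = Φ((10 - 9)/1.00) = 84.1%, within 2 points of the stated 82.8%.

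No figure in the plan is in dispute.

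**Step 3. Shift in one arm's Week 46 mean.** The documents give neither the number of misclassified patients (k) nor the gap between the off-drug weight change and the on-drug prediction (d). I assume k = 1 to 5, all in one arm, and d = 4 to 8 percentage points. The shift is approximately k × d / 70.

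| k | d = 4 | d = 8 |
|---|---|---|
| 1 | 0.06 | 0.11 |
| 2 | 0.11 | 0.23 |
| 3 | 0.17 | 0.34 |
| 5 | 0.29 | 0.57 |

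The SE of a simple difference from placebo is 7 × √(2/70) = 1.18, so the range is 0.05 to 0.48 SE.

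**Step 4. Effect on probability of success if every case is an uncensored stop at 4.8 mg.** In the linear fit the top arm has weight 4.8 × (4.8 - 2.28) / 16.128 = 0.75.

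- k = 1, d = 4: 0.75 × 0.057 = 0.043, and Φ(1 - 0.043) = 83.1%.
- k = 5, d = 8: 0.75 × 0.571 = 0.429, and Φ(1 - 0.429) = 71.6%.

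**Step 5. Spread and sign.** With five cases spread one per arm, each arm moves by only 0.06 to 0.11 points, and any shift in placebo offsets part of the difference. If off-drug patients weigh more than predicted on drug, uncensored pandemic stops pull an active arm toward no effect and wrongly censored unrelated stops push it the other way. Errors of both kinds would partly cancel.

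**The case against.** The case for leaving the rule alone has weight. A SAP must turn an estimand into a data rule, and the indirect limb names much the same causes as the protocol. Asking for clear evidence before setting observed data aside is a reasonable default. The 7.9 query is expressly for safety tables. The only further term that the documents name is an unconfirmed case, whereas the SARS-CoV-2 stopping criterion in protocol 3.3.4.1 refers to PCR-confirmed infection. The SAP does not say that COVID-19 in 7.4.1 means one coded preferred term. SAP 7.4 plans all-data, COVID-censored and on-treatment summaries, so some sensitivity will be visible descriptively. Parts of 7.9, and the section 7.4.2 that SAP 6.6 cites, are absent from the public copy.

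These points limit the concern but do not remove it. Nothing visible says how to treat a COVID-19 comment filed under another reason, or a suspected case, and nothing ties the AE to the stop.

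A reader might also infer that quarantine stops are bound to be lost through the two-missed-dose rule in protocol 4.1.4 ("In case of consecutive 2 skipped doses, the treatment discontinuation should be considered (general rule")). The documents do not support that. The same bullet refers pandemic situations to the sponsor for an alternative and lets the patient restart. The rule on more than 4 skipped doses carries no such exception, so it is the more plausible route.

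**Conclusion.** The mismatch is real and can be read from the text: protocol 7.2.2, SAP 7.4.1 and SAP 7.9 do not pick out the same patients. It is a low-severity point. Under the assumptions above, the shift in one arm's mean runs from negligible (0.06 points) to noticeable against the 1.0 point planned margin (0.57 points). The upper end needs five misclassified patients in a single arm, all with weights beyond 28 days after last dose and all misclassified in the same direction. Nothing in the documents ties quarantine, supply or site closure to blinded dose, so such clustering is not the expected case.

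Two stronger readings should be resisted. One is that genuine pandemic stops will stay uncensored. The documents support only that they can, because the eCRF reason categories and the number of such stops are not given. The other is that the rule is simply too narrow. The direct limb can also censor too much.

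**What to change.** Amend SAP 7.4.1 as follows:

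- **Direct limb:** an AE within the SARS-CoV-2 query of SAP 7.9 that is recorded as leading to treatment discontinuation. State whether 'Suspected COVID-19' counts. The link to the stop also closes the over-censoring gap.
- **Indirect limb:** any End of Treatment reason whose comment, or linked COVID-19 deviation record, gives a pandemic cause.
- **Patient list:** classify early stops by cause and finalise the list blinded before database lock.

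The cost is two SAP sentences and a short blinded listing review. The query already exists, SAP 7.9 already plans a table of these AEs leading to discontinuation, and protocol 6.1 already requires COVID-19 deviations to be documented and their implications for the analysis considered.

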7.2.2 Primary endpoint analyses

The analysis for PoCC and dose-finding will be performed using multiple comparison and modelling techniques (MCPMod) [R10-1424] whereby several possible dose response models (patterns) will be evaluated, while keeping full control of the type I error at 2.5% (one-sided) to identify the best-fitting model or subset of models.

To account for repeated body weight measurements over time and for inclusion of baseline covariates in the model, a mixed model for repeated measures (MMRM) analysis will first be carried out. The MMRM will include fixed effects for baseline body weight and baseline by visit interaction as continuous covariates, and treatment, gender, visit and treatment-by-visit interaction as factors. Unstructured covariance will be used to model the relationship between pairs of endpoint measurements taken at different visits on the same patient. The Kenward-Roger approximation will be used to estimate the denominator degrees of freedom. The TSAP will specify approaches to be taken to resolve possible non-convergence issues, including if necessary, the selection of a simpler covariance structure.

Covariate-adjusted fixed effect estimates of mean percentage change in body weight at Week 46 for each treatment group and the covariance matrix will be extracted from the MMRM fit. These will be used for the subsequent MCPMod analysis.

For the PoCC testing and for the sample size calculation, the basic shape of each of the models to be tested must be pre-defined. The following model assumptions and resulting graphs (Figure 7.2.2: 1) have been selected to cover a plausible and diverse range of monotone dose response patterns, with placebo mean response assumed to be zero and the mean response at the highest BI 456906 dose assumed to be -10.0 (i.e. a percentage reduction from baseline in body weight of 10%):

- Linear
- Exponential: 50% of maximum effect achieved at dose 3.6 mg
- Emax1: 90% of maximum effect achieved at dose 4.8 mg

- Emax1: 70% of maximum effect achieved at dose 4.8 mg
- Sigmoid Emax: 50% of maximum effect achieved at dose 2.4 mg; 90% of max effect achieved at dose 4.8 mg

[figure not shown]

Figure 7.2.2: 1 Dose response patterns considered for the MCPMod analysis.

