7.4 RANDOMISATION

BI will arrange for the randomisation and the packaging and labelling of trial medication. The randomisation list(s) will be generated using a validated system, which involves a pseudo-random number generator so that the resulting treatment will be both reproducible and non-predictable. The block size will be documented in the Clinical Trial Report (CTR). Access to the codes will be controlled and documented.

Patients will be randomised in blocks using equal allocations to one of 5 double-blind treatment groups. Randomisation will be performed at the start of the dose escalation period at Day 1, Visit 2 (starting dose and timing of dose escalation as outlined in [Table 4.1.4: 1](#)), with allocation to one of the following target maintenance period treatments:

- Placebo once weekly
- BI 456906 0.6 mg once weekly
- BI 456906 2.4 mg once weekly
- BI 456906 3.6 mg once weekly
- BI 456906 4.8 mg once weekly

Randomisation will be stratified by gender. It is anticipated that no more than 70% women will be randomised.

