Prior to applying the visit windows specified below, it will first be determined whether the data record is on-treatment, as defined in [Section 6.1.6](#), for summaries or analysis which require this approach.

Unscheduled and repeat assessments (where relevant/available) are eligible for inclusion in visit windows.

For all variables except 12-lead ECG, if a patient has more than one non-missing value within the same visit window, the value closest to the target day will be selected. If two non-missing values are the same distance from the target day, the earlier of the two values will be selected.

For 12-lead ECG (only), scheduled visits take precedence over unscheduled visits. Once this rule has been applied, the measurement closest to the target day will be used. If there are two observations which have the same difference in days to the planned day (but are not on the same day), the later of the two values will be selected.

Derivation of last, minimum and maximum values where relevant in safety analyses will consider all available values, regardless of whether they were selected in the visit window.

The derivation of the maximum value of an ECG interval (or worst case of the morphological assessment, if applicable) will consider all on-treatment values (whether or not selected in any time window; see [Section 6.1.6](#) for definition of on-treatment).

Two different situations are envisaged, which are described in the following tables:

- Visit windows for variables scheduled to be assessed at all or many visits
- Visit windows for variables with a sparse visit schedule.

Table 6.7: 1 Visit windows for variables scheduled to be assessed at all or many visits

Period	Time Point	Target Day	Visit Window
Dose escalation	Week 2	15	2-21
	Week 4	29	22-35
	Week 6	43	36-49
	Week 8	57	50-63
	Week 10	71	64-77
	Week 12	85	78-91
	Week 14	99	92-105
	Week 16	113	106-119
	Week 18	127	120-133
Maintenance	Week 20	141	134-154
	Week 24	169	155-182
	Week 28	197	183-210
	Week 32	225	211-238
	Week 36	253	239-266
	Week 40	281	267-301
	Week 46	323	≥ 302

The relevant variables are expected to include body weight measured at the clinic and BMI derived from this, vital signs, routine non-fasting laboratory safety variables, 12-lead ECG and the mental health questionnaires (C-SSRS, PHQ-9).

These visits windows will also be used for waist circumference, although this is not scheduled to be captured at all weeks displayed.

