Unstructured covariance will be assumed to model the relationship between pairs of measurements taken at different weeks on the same patient. If the model fails to converge, all reasonable attempts will first be made to encourage convergence on the specified model with all scheduled weeks included. These attempts will include (but may not be limited to) first adjusting singularity options, then increasing the maximum number of convergence iterations, using the Fisher scoring algorithm for the early iterations, and providing starting values for the covariance parameters. Only if none of these options is successful will further options which simplify the fitted model be considered. In this case, reduction in the number of time points (e.g. by omitting one or more weeks during the dose escalation period) will be considered before any attempt is made to simplify covariance structure. If the latter needs to be considered as a last resort, simpler covariance structures will be evaluated in a nested sequence, where each covariance matrix is a special case of all which have been tried before.

Adjusted means will be calculated from the MMRM using the observed margins approach, in which the contribution of model factors to the estimate is weighted proportionally to the presence of these factors in the data (noting in particular that unequal proportions of males and females are expected in this trial by design).

A summary table will be produced of the MMRM results at each time point, including adjusted means and their standard errors for each treatment group, and including adjusted mean differences from placebo for each BI 456906 dose group and their 95% confidence intervals.

Adjusted means from the MMRM will also be displayed graphically over time to assess the onset of effect over time.

Adjusted means at Week 46 for each treatment group and the associated covariance matrix for those adjusted means will be extracted from the MMRM for use in the subsequent dose finding analysis using multiple comparison and modelling (MCPMod) techniques, described below:

MCPMod

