An MMRM will be fitted in turn to each continuous secondary endpoint variable at each scheduled week. The MMRM will include the same model terms as for the primary analysis described in [Section 7.4.1](#), except that, where necessary, baseline body weight will be replaced by the baseline corresponding to the relevant endpoint. Unstructured covariance will be assumed to model the relationship between pairs of measurements taken at different weeks on the same patient. If the model fails to converge, similar attempts to address this will be made as for the primary analysis.

A summary table will be produced for each continuous secondary endpoint of the MMRM results at each time point, including adjusted means (using the observed margins approach) and their standard errors for each treatment group, and adjusted mean differences from placebo for each BI 456906 dose group and their 95% CIs.

Adjusted means from the MMRM for each continuous secondary endpoint will also be displayed graphically over time to assess the onset of effect over time.

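### The primary MMRM holds the gender effect constant over visits, so the stratification factor is largely unadjusted at Week 46; the cost is small and one model term removes it.

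*SAP*

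**What the plan says.** Beside a linear covariate for baseline weight, SAP 7.4.1 lists "treatment, gender, visit, treatment by visit interaction and baseline by visit interaction as factors". Protocol 7.2.2 has the same structure: a baseline-by-visit interaction, then "treatment, gender, visit and treatment-by-visit interaction as factors". Neither document has a gender-by-visit term.

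The surrounding provisions are:

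- Protocol 7.4: "Randomisation will be stratified by gender", and "It is anticipated that no more than 70% women will be randomised".
- SAP 7.4.1, covariance: "Unstructured covariance will be assumed to model the relationship between pairs of measurements taken at different weeks on the same patient".
- SAP 7.4.1, dose finding: "Adjusted means at Week 46 for each treatment group and the associated covariance matrix for those adjusted means will be extracted from the MMRM". No other visit enters MCPMod.
- SAP 7.4.1 uses observed margins for the adjusted means. This sets the male and female weights in those means. It does not let the gender effect change over time.
- SAP 7.5.2, continuous secondary endpoints: "The MMRM will include the same model terms as for the primary analysis", with the relevant baseline substituted.

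**The concern.** A single gender coefficient has to serve every visit from Week 2 to Week 46. For a percentage change that starts at zero, any gender difference must start near zero and build up, and so must the variance. A common coefficient is then estimated mainly where the data are least variable, at the start, and applied at Week 46, where the difference would be largest.

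Two things are at stake. First, the design stratifies on gender but the Week 46 standard errors get little credit for it. Second, where Week 46 weights are missing, the model's prediction uses a gender effect that is too small. If missingness differs by gender and arm, part of the gender effect can leak into the dose contrast.

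**Working it through.** **The plan's own figure.** Protocol Table 7.5:1, at a true maximum effect of -10.0% with 70 per arm and SD 7.0%, gives 82.8 / 83.3 / 83.8 / 83.3 / 89.0%, average 84.4%. Simulating five arm means with variance 49/70, the contrast test at one-sided 2.5% and the three success criteria (10,000 runs per shape) gives 82.5 / 82.6 / 83.5 / 83.2 / 89.8%, average 84.3%. The figure is reproduced.

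**Inputs from the documents.** The 16 post-baseline windows come from the SAP 6.7 table headed "Visit windows for variables scheduled to be assessed at all or many visits": Weeks 2 to 20 every two weeks, then 24, 28, 32, 36, 40 and 46. The Week 46 SD is 7.0% (Protocol 7.5). Women are at most about 70%.

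**Assumed, because the documents are silent.** The gender difference at Week 46 (2 to 5 points), its growth over time, and the covariance over time.

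**Formula.** With treatment and baseline weight free at each visit, the common gender coefficient is

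γ = (1'Σ⁻¹g) / (1'Σ⁻¹1),

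where g is the vector of gender differences by visit and Σ is the covariance matrix.

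**A case that can be done by hand.** If variance accumulates in proportion to time with independent increments, all the weight falls on the first visit. The Week 2 SD is 7 × √(2/46) = 1.46. As a share of the Week 46 gender difference, γ is then:

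- linear growth: 2/46 = 4%
- saturating growth (15-week constant): (1 − e^(−2/15)) / (1 − e^(−46/15)) = 0.125/0.953 = 13%
- square-root growth: √(2/46) = 21%

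**Why the sign can reverse.** With Weeks 2 and 46 only, the Week 46 weight is (s₁² − ρs₁s₂) / (s₁² + s₂² − 2ρs₁s₂). This is negative whenever ρ exceeds s₁/s₂ = 1.46/7 = 0.21. At ρ = 0.5 it is (2.13 − 5.11) / (2.13 + 49 − 10.22) = −0.073. With linear growth, γ is then 1.073 × 0.043 − 0.073 = −0.026 of the Week 46 difference.

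**All 16 visits, range of covariances.**

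| Covariance | γ as share of Week 46 difference |
|---|---|
| Accumulating variance (Week 2 weight 0.73 to 1.00, Week 46 weight −0.03 to 0.00) | 3 to 24% |
| SD growing from 1.0–2.5, AR-type or exchangeable correlation | −31 to +10% |
| SD 7.0 at every visit (implausible for weight change) | 43 to 67% |

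**Fitted MMRMs (65% women, accumulating variance).** A true difference of 3 points at Week 46 gives a common coefficient of 0.4 to 0.5; with gender by visit the Week 46 estimate is 2.8 to 3.1. A true 5 gives about 0.8 against 4.8 to 5.1. Baseline weight by visit takes up part of the remainder. With an assumed 17 kg gender gap in mean weight and a fitted slope of 0.49 per 18 kg, that is 0.49 × 17/18 = 0.46 of the 3 points.

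**Standard errors.** If gender were wholly unadjusted, the variance it adds is 0.7 × 0.3 × d² = 0.21d². The inflation is √(49/(49 − 1.89)) = 1.020 at d = 3 and √(49/(49 − 5.25)) = 1.058 at d = 5, an upper bound of 2.0 to 5.8%. Fitted models for 4.8 mg minus placebo give less: 1.189/1.174 = 1.3% at 3 points and 1.246/1.205 = 3.4% at 5 points. A separate simulation gave 0.7, 1.6 and 2.8% at 2, 3 and 4 points.

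**Chance imbalance.** One extra woman in an arm of 70 shifts that arm by at most 3/70 = 0.04 to 5/70 = 0.07 points.

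**Missing data.** With 35 to 45% of women and 15% of men missing on active arms and 15% on placebo, the two models differ at Week 46 by about 0.05 to 0.18 points. A separate scenario (30% of women and 10% of men on 4.8 mg, 8% on placebo, 3-point difference) gave 0.14 to 0.16.

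**Probability of success with the term added.** Taking the SD down to √(49 − 1.89) = 6.86 or √(49 − 5.25) = 6.61 moves the simulated average from 84.3% to 85.0% or 85.6%.

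**The case against.** The strongest reply is that the practical effect is close to nil. Stratified randomisation keeps gender nearly balanced, so with complete data the dose contrasts are essentially unbiased. The standard-error cost is small and conservative, and Protocol 7.1 says that no confirmatory testing is done. All of this stands.

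The missing-data shift rests on stacked assumptions, none of them in the documents. The primary strategy also keeps weights taken after non-pandemic discontinuation. Protocol 6.2.3 asks for four-weekly weighing and a Week 46 visit or home weight, so stopping treatment need not mean missing data. Under an unstructured covariance, a missing Week 46 value is predicted partly from the patient's own trajectory, which already carries some of the gender difference. These points limit the shift but do not remove it.

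Three stronger readings are tempting, and the documents do not support them:

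- **About 4 points of probability of success lost.** A reader might apply the slope of Table 7.5:1, (84.4 − 70.5)/0.5 = 27.8 per point, to a 0.15-point shift. That table moves the whole true curve. A shift at 4.8 mg alone is diluted by the model fit: simulated, 0.15 points there takes the average from 84.4% to 81.7%, still above 80%, and only under the assumed missingness.
- **Gender is adjusted at its Week 2 size.** This holds for accumulating variance but not generally. Under other growing-variance covariances the coefficient is smaller or has the wrong sign.
- **SAP 6.6 contradicts itself.** The responder imputation lets gender differ by week, yet SAP 6.6 says it shares the MMRM's missing-at-random assumption. Sharing that assumption is not a claim to use the same model, and the two already differ: the imputation works on actual weights.

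**Conclusion.** The point holds as a small loss of efficiency. In every growing-variance case examined, Week 46 gets almost no weight in the gender coefficient and at least about three quarters of any Week 46 gender difference stays unadjusted, apart from what baseline weight by visit absorbs.

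Its size depends on a gender difference that the documents do not give. At 2 to 5 points, Week 46 standard errors are about 1 to 4% too wide. If missing data differ by gender and arm, a dose effect can move by about 0.05 to 0.18 points, up or down according to the pattern. Type I error, the proof-of-concept test and the stated probability of success are not threatened. If gender has no effect on percentage weight change, nothing is lost.

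The growing-variance argument carries over directly to absolute weight change. It is weaker for blood pressure, whose change need not start with a small variance.

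**What to change.** Add a gender-by-visit interaction to the primary MMRM in SAP 7.4.1, and through the shared terms to the secondary-endpoint MMRMs in SAP 7.5.2. Keep the observed-margins adjusted means.

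The cost is 16 − 1 = 15 fixed-effect parameters, beside the 16 × 17/2 = 136 covariance parameters already planned, with 350 patients. The existing non-convergence steps in SAP 7.4.1 can stay as they are.

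This is not a change to SAP 7.4.1 alone, because the protocol states the model terms in its synopsis and in 7.2.2. Record the departure in SAP Section 4, before database lock and unblinding.
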